The aim of this study is to investigate the hemodynamic effects of ketamine and etomidate in the setting of rapid sequence intubation.

OBJECTIVES:

The objective of this study is to determine if ketamine or etomidate has a better hemodynamic profile in patients undergoing rapid sequence intubation.

HYPOTHESIS:**Primary Hypothesis:**

Compared to etomidate, ketamine will show an improved hemodynamic profile in patients undergoing rapid sequence intubation.

STUDY DESIGN:

This study will be a prospective randomized controlled trial evaluating the hemodynamic response in adult patients (greater than or equal to 18 years of age) undergoing rapid sequence intubation (RSI).

STUDY SETTING:

This study will be a single-center study to include pre-hospital RSI performed by New Hanover Regional Medical Centers (NHRMC) emergency transport service providers as well as emergency medical physicians performing RSI at the NHRMC emergency department located on the main hospital campus.

STUDY POPULATION:

Adult patients age 18 and greater who are not pregnant and require rapid sequence intubation will be part of the study population. Patients may require rapid sequence intubation to secure his or her airway for a myriad of reasons to include trauma, impending respiratory failure, septic shock. These patients often have labile hemodynamics in the time period surrounding intubation and the drugs used may influence this hemodynamic response.

This study is projected to treat approximately 400 subjects. Our goal is to have 200 patients in the ED settings, with 100 having etomidate and 100 having ketamine. In the pre hospital setting there will be 100 having etomidate and 100 having ketamine.

ELIGIBILITY CRITERIA:**Inclusion Criteria:**

Adult patients age 18 and greater who require RSI for any indication.

Exclusion Criteria:

1. Children under the age of 18 as these patients have a different hemodynamic profile than adults and would require a separate study to clearly elucidate the effect of ketamine or etomidate during RSI.

2. Pregnant women of any age as these patients also have a different hemodynamic profile than adult patients and would require a separate study to clearly elucidate the effect of ketamine or etomidate during RSI.
3. Patients with a known hypersensitivity to ketamine or etomidate will not be administered that respective agent and will not be crossed over into the opposite group.

STUDY OUTCOMES:**Primary Outcomes:**

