The primary outcome will be the incidence of post RSI hypotension between patients undergoing RSI with ketamine versus patients undergoing RSI with etomidate. Post RSI hypotension will be defined as a 20% decrease in the systolic blood pressure from a patient's baseline.

Secondary Outcome(s):

Secondary outcomes will include: incidence of first pass intubation success, incidence of supplemental blood pressure agents (e.g. vasopressors) required post-RSI, time to additional sedative use

STUDY PROCEDURES:**Recruitment of participants:**

Patients who require rapid sequence intubation are critically ill and are not capable of making medical decisions at the time of the procedure. During these critical moments, surrogate decision makers are rarely, if ever present and this procedure is performed as a life-saving measure to allow for further medical therapies. Informed consent of the patient nor a surrogate decision maker is possible at the time of the procedure.

Randomization:

Randomization will be assigned by calendar day beginning at midnight, with etomidate being administered to all RSI patients on even calendar days and ketamine being administered to all RSI patient on odd calendar days.

Study Procedure:

Etomidate will be dosed at a standard 0.3 mg/kg and ketamine will be dosed at a standard 2 mg/kg for the purposes of this study. Data will be collected from the pre-hospital electronic medical record for patients undergoing RSI in the pre-hospital setting and from the inpatient electronic medical record for patients undergoing RSI in the emergency department. Data extracted from each record will include ketamine or etomidate dosages and time of delivery, sets of vital signs prior to and post-intubation, number of intubation attempts, number of lost airways, dose and timing of any additional medications, requirement for additional fluid or blood product administration, indication for advanced airway placement, admitting service, lab data, past medical history, and standard patient demographics. The hemodynamic response will be measured by assessing hemodynamics for two measurements prior to administration of ketamine or etomidate and for two measurements up to fifteen minutes post administration or

until an additional sedative medication is administered. (Please separate sheet that will be placed in RedCap once IRB approval has been obtained).

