Ketamine and etomidate are immediately available for RSI in the pre-hospital and hospital settings and are both currently standard of care for RSI at our facility.

Data Storage:

All data will be kept in the secure database RedCap. Only study staff will have access to the database.

Safety considerations/Patient safety:

Etomidate and ketamine are both frequently used in the pre-hospital and emergency department setting with an acceptable safety profile. Etomidate has described adverse reactions to include adrenal suppression, pain at the injection site, nausea and vomiting, and nystagmus. Ketamine has described adverse reactions to include confusion/delirium, hallucinations, vivid imagery, bradycardia, increased blood pressure, nausea and vomiting, pain at the injection site, laryngospasm and nystagmus. These adverse reactions have not precluded use in routine clinical care. If a patient has a known hypersensitivity or allergy to either medication, they will not be given that medication.

STATISTICAL CONSIDERATIONS AND DATA ANALYSIS:

Sample size and statistical power: To maintain 80% power with a probability of 0.05, 200 patients will be needed in each arm to detect at 25% difference in SBP (baseline to post drug administration effects)

Statistical methods:

Data will be analyzed using SPSS with a p-value of less than 0.05 being considered significant. We will consider a 20% decrease in systolic BP from a patient's baseline as significant, and will compare the incidence of post RSI hypotension between the two groups. Several a priori subgroups will be evaluated to include patients greater than 70 years of age, trauma patients requiring RSI, and those patients whose shock index is less than 0.9 versus those whose shock index is greater than 0.9.

OUTCOMES AND SIGNIFICANCE:

The results from this study will help elucidate a sedative agent that is most appropriate in unstable patients across a spectrum of clinical scenarios to include cardiac dysfunction, severe sepsis with septic shock, trauma and the elderly.

REFERENCES:

Bijker JB, van Klei WA, Kappen TH et al. Incidence of intraoperative hypotension as a function of the chosen definition. *Anesthesiology*. 2007;107:213-220.

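### The 80% power claim is for a 25% difference in SBP, but the primary outcome is the incidence of a 20% SBP fall, so power for the primary comparison is not established

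*Combined protocol and SAP*

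**What the plan says.** Under STUDY OUTCOMES, Primary Outcomes: "The primary outcome will be the incidence of post RSI hypotension", compared between the ketamine and etomidate patients. The event is then defined: "Post RSI hypotension will be defined as a 20% decrease in the systolic blood pressure", relative to the patient's own baseline. Statistical methods repeats that the investigators "will compare the incidence of post RSI hypotension between the two groups".

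The only power statement is under Sample size and statistical power. It opens "To maintain 80% power with a probability of 0.05" and continues "200 patients will be needed in each arm to detect at 25% difference in SBP (baseline to post drug administration effects". STUDY POPULATION gives a matching total of about 400: 100 per drug in the emergency department and 100 per drug pre-hospital.

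The available text states no expected incidence of hypotension in either arm, no SD for blood pressure or its change, no named test and no sidedness. The primary hypothesis is directional ("ketamine will show an improved hemodynamic profile in patients undergoing rapid sequence intubation"), so it does not settle whether the 0.05 is one-sided or two-sided.

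**The concern.** The parenthesis in the power sentence describes a blood pressure change from before to after the drug. The primary analysis compares proportions of patients. Power for one does not carry over to the other without an assumed incidence in each arm, and the plan supplies none. The 25% in the power sentence is also not the 20% that defines the event.

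What is at stake is how the result will be read. The background section says that the site's own earlier retrospective comparison was non-significant and underpowered, and it calls for a randomized trial to settle superiority. If this trial finds no significant difference, a reader needs to know what difference in incidence it could have detected. The plan does not say.

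**Working it through.** **Inputs from the plan.** Power 80%; alpha 0.05; 200 per arm; equal arms; effect given as 25%. Sidedness is unstated, so I use two-sided 0.05 (z = 1.960) unless noted. For 80% power, z = 0.842.

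**Inputs assumed, because the plan gives none.** Etomidate incidence 20 to 50%; mean SBP 120 mmHg; SDs as shown.

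**Formulas.**
- Two proportions, pooled variance, no continuity correction: n per arm = [1.960·√(2p̄(1−p̄)) + 0.842·√(p1(1−p1) + p2(1−p2))]² / (p1−p2)², where p̄ is the mean of p1 and p2.
- Two means, normal approximation: n per arm = 2·[(1.960 + 0.842)·SD/difference]².

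**Step 1. Can the plan's 200 be reproduced?** Not from its stated inputs alone, so I tried each reading of 25%.

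*(a) 25 percentage points in incidence.* The largest requirement is at 62.5% vs 37.5%: [1.960·0.7071 + 0.842·0.6847]² / 0.0625 = 61.6, so 62 per arm (70 with continuity correction). Other pairs need fewer: 27 (25 vs 0%), 36 (30 vs 5%), 49 (40 vs 15%), 58 (50 vs 25%). No variant gives 200. The lowest power at 200 per arm is 99.92%.

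*(b) 25% relative reduction in incidence.* For 30% vs 22.5%: [1.960·0.6222 + 0.842·0.6200]² / 0.075² = 539.1, so 540 per arm. In full:

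| Assumed etomidate incidence | Ketamine incidence | n per arm for 80% power | Power at 200 per arm |
|---|---|---|---|
| 20% | 15% | 906 | 25.9% |
| 30% | 22.5% | 540 | 39.9% |
| 40% | 30% | 356 | 55.5% |
| 50% | 37.5% | 247 | 71.4% |

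This reading gives 200 only at an etomidate incidence of about 55.9%, or about 49.1% if the test is one-sided.

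*(c) 25% difference between arms in mean SBP.* 25% of 120 mmHg is 30 mmHg. With SD 15, n = 2·(2.802·15/30)² = 3.9, so 4 per arm. With SD 50, n = 43.6, so 44 per arm.

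*(d) 25% difference in the baseline-to-post change.* This is closest to the parenthesis. For a mean change of 15 to 30 mmHg and SD of 15 to 30 mmHg, the requirement runs from 63 per arm (difference 7.5, SD 15) to 1,005 (difference 3.75, SD 30). It reaches 200 with, for example, a mean change of 24 mmHg (difference 6) and SD 21.4.

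*(e) Standardised difference.* 200 per arm detects 2.802·√(2/200) = 0.280 SD. A difference of 0.25 SD needs 252 per arm two-sided and 198 one-sided.

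Some readings therefore reach 200, but each relies on an input that the plan does not state. Readings (c), (d) and (e) concern blood pressure itself, not the primary outcome.

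**Step 2. What can 200 per arm detect on the primary outcome?** Solving the two-proportion formula for p2 at 80% power, two-sided 0.05:

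| Etomidate incidence (assumed) | Detectable ketamine incidence | Absolute difference |
|---|---|---|
| 20% | 10.0% | 10.0 points |
| 30% | 18.1% | 11.9 points |
| 40% | 26.8% | 13.2 points |
| 50% | 36.2% | 13.8 points |

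Check on the first row: 20% vs 10% gives [1.960·0.5050 + 0.842·0.5]² / 0.01 = 199 per arm.

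**The case against.** The strongest reply is that the phrase about SBP is loose wording for incidence. The background section describes the site's earlier study as a count of patients whose SBP fell, in similar language, and the paragraph after the power sentence compares incidence. On that view nothing is miscalculated; the inputs are simply incomplete. A related point is that part of the front matter was not available for review, and the earlier study could have supplied an incidence.

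Some of this stands. No figure in the paragraph is shown to be arithmetically false, several readings do reach 200, and the absence of an incidence can be asserted only for the text available. But the loose-wording reading does not supply the missing incidence. As a 25% relative reduction it needs an etomidate incidence of about 56% (about 49% one-sided); as 25 absolute points it cannot give 200 at all. The sample size paragraph appears intact and contains none of these inputs.

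It is also fair to say that power well above 80% harms no one, and that the low power figures rest on assumed incidences combined with the relative reading. They show how wide the uncertainty is, not that the trial is too small.

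**Conclusion.** The concern holds. The one power statement addresses a difference in SBP, the primary comparison is of the incidence of a 20% SBP fall, and nothing in the available text connects them. Power of 80% is therefore not established for the primary outcome. At 200 per arm it ranges from about 26% (25% relative reduction from 20%) to above 99.9% (25 absolute points), depending on what 25% means and on an incidence that the plan does not give.

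These figures assume two-sided 0.05, the pooled-variance formula without continuity correction, 200 analysed patients per arm, independent patients and complete data. The last two assumptions are not guaranteed by the design: "Randomization will be assigned by calendar day beginning at midnight", so patients treated on the same day share an arm, and post-drug measurement may run only "until an additional sedative medication is administered". Neither feature is modelled here.

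**What to change.** Replace the sample size sentence with one about the primary outcome, and drop the claim of 80% power for a 25% difference in SBP. The new text should give the assumed etomidate incidence of post-RSI hypotension and its source, the absolute difference to be detected, the test, and a two-sided alpha of 0.05.

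If 200 per arm is kept, a suitable form is: *With 200 patients per arm and a two-sided alpha of 0.05, a comparison of two proportions by [named test] has 80% power to detect a fall in the incidence of post-RSI hypotension from [x]% with etomidate to [y]% with ketamine. The etomidate incidence is taken from [source]. The calculation assumes independent patients and complete outcome data.* The pairs that fit are about 20% vs 10%, 30% vs 18%, 40% vs 27% and 50% vs 36%. The sponsor should choose the row that its own data support, not list all four, and confirm the pair for the test it names.

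The cost is one paragraph; the correction itself adds no patients. If the sponsor wants to detect a smaller difference than these, the number per arm must be recalculated from that difference and could exceed 200, for example 540 per arm for 30% vs 22.5%.

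### The primary comparison of hypotension incidence makes no allowance for assignment by calendar day and does not use recorded baseline SBP or setting as covariates

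*Combined protocol and SAP*

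**What the plan says.** The protocol and SAP are one document.

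- **Endpoint** (Primary Outcomes): "Post RSI hypotension will be defined as a 20% decrease in the systolic blood pressure", measured from the patient's own baseline.
- **Analysis** (Statistical methods): "Data will be analyzed using SPSS with a p-value of less than 0.05 being considered significant", and the plan "will compare the incidence of post RSI hypotension between the two groups". Subgroups follow for age over 70, trauma, and shock index below or above 0.9. No test, sidedness, effect measure, confidence interval, covariate or clustering term is named.
- **Assignment** (Randomization): "Randomization will be assigned by calendar day beginning at midnight", with etomidate on even days and ketamine on odd days for all RSI patients.
- **Data** (Study Procedure): hemodynamics are taken at "two measurements prior to administration of ketamine or etomidate", and the extracted items include "ketamine or etomidate dosages and time of delivery, sets of vital signs prior to and post-intubation". The source record identifies the setting: "Data will be collected from the pre-hospital electronic medical record for patients undergoing RSI in the pre-hospital setting", and the inpatient record serves ED patients.
- **Setting targets** (Study Population): "Our goal is to have 200 patients in the ED settings, with 100 having etomidate and 100 having ketamine", and the same split pre-hospital.
- **Sample size**: 200 patients per arm, with no term for assignment by day.

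**The concern.** Two features of the design are missing from the analysis. First, the unit of assignment is the day. If patients treated on the same day resemble each other (same crews, same physicians, same case mix), a test that treats them as independent understates the standard error. Second, baseline SBP probably predicts whether SBP falls by 20%, and event risk may differ between the ED and the pre-hospital service. A model using both could be more precise at almost no cost.

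With no model fixed, the choice of test, sidedness and covariates also stays open until the data are in hand. The hypothesis is worded in one direction, so sidedness is a real ambiguity.

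**Working it through.** **The plan's own figure.** The 200 per arm (80% power, 0.05, a 25% difference in SBP) cannot be reproduced, because no SD or control incidence is given. The checks below take 200 per arm as fixed and use risk pairs at which it gives about 80% power. Patients per day, ICC, event rates and pre/post correlation are not in the documents; all are assumed.

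**1. Day clustering.** If daily counts are Poisson with mean λ, a patient shares the day with λ others on average. The design effect is therefore DE = 1 + λ × ICC. The true two-sided alpha of an unclustered test is 2 × [1 − Φ(1.96/√DE)].

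| λ per day | ICC | DE | √DE | True alpha |
|---|---|---|---|---|
| 1 | 0.01 | 1.01 | 1.005 | 0.051 |
| 3 | 0.01 | 1.03 | 1.015 | 0.053 |
| 1 | 0.05 | 1.05 | 1.025 | 0.056 |
| 3 | 0.05 | 1.15 | 1.072 | 0.068 |

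Simulation under the null (alternating days, 200 per arm, risk 0.30, 6,000 runs per cell, Monte Carlo error about 0.003) compared the unclustered test with the adjusted analysis using day-clustered standard errors:

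- 3 per day, ICC 0.05: 0.063 to 0.064 against 0.050.
- 3 per day, ICC 0.01: 0.055 to 0.057 against 0.057 to 0.059.
- 1 per day: 0.051 to 0.055 against 0.052 to 0.053.

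The difference is clear only at the top of the range.

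**2. Baseline SBP.** Let r be the pre/post correlation and k the post/pre SD ratio, with normal readings. The event is post-drug SBP below 0.8 × baseline. Its probit slope per SD of baseline is (0.8 − rk) / (k√(1 − r²)). With k = 1:

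- r 0.8: 0/0.6 = 0, odds ratio (OR) per SD about 1.0
- r 0.6: 0.2/0.8 = 0.25, OR about 1.5
- r 0.5: 0.3/0.866 = 0.35, OR about 1.8
- r 0.3: 0.5/0.954 = 0.52, OR about 2.4

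Simulated power in %, crude test / adjusted with day-clustered standard errors (200 per arm, 5,000 runs):

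| r | 0.30 v 0.18 | 0.20 v 0.10 | 0.40 v 0.27 | Gain (points) |
|---|---|---|---|---|
| 0.8 | 80.3 / 81.0 | 80.4 / 80.7 | 78.6 / 79.3 | 0.3 to 0.7 |
| 0.6 | 80.7 / 82.8 | 80.8 / 81.9 | 78.5 / 80.0 | 1.1 to 2.1 |
| 0.5 | 81.4 / 83.5 | 80.5 / 81.8 | 78.1 / 81.1 | 1.3 to 3.0 |
| 0.3 | 81.1 / 85.8 | 81.4 / 85.7 | 79.7 / 85.2 | 4.3 to 5.5 |

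At r 0.8 variance is not reduced, so that small gap is test size; it is also contained in the other rows. Without clustering, null rejection was 0.047 to 0.054 crude and 0.050 to 0.060 adjusted.

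The result is sensitive to k. At k = 0.8 and r 0.3 the slope is 0.56/0.763 = 0.73 and the OR per SD about 3.5, so the gain is larger. At k = 1.2 the slope is zero at r = 0.8/1.2 = 0.67, so the gain vanishes at a lower correlation.

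**3. Setting.** If the 100/100 targets are met, or both settings tilt the same way, there is no shift. Suppose the ED splits 110 v 90 and event risk differs by 5 to 15 points between settings:

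- Pre-hospital 100/100: share difference 110/210 − 90/190 = 0.050, a shift of 0.25 to 0.75 points.
- Pre-hospital 90 v 110: share difference 110/200 − 90/200 = 0.100, a shift of 0.5 to 1.5 points. With 200 per arm and 200 per setting, a split at least this large has hypergeometric probability 0.057, ignoring day clustering.

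**4. Which baseline.** Two pre-drug readings are taken, but the baseline is not defined. Illustration: 140 then 110 before the drug and 96 after is a fall of 31% from the first reading, 23% from their mean (125) and 13% from the last. The same patient is an event or not depending on the choice, so the covariate and the endpoint need one definition.

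**The case against.** The strongest reply is that the harm is small and every input is assumed. This largely stands. Over most of the range the clustered, adjusted test is no closer to 0.05 than the plain one, and it can itself be slightly liberal. Covariate adjustment is an efficiency recommendation, not the correction of an error, and its gain depends on the SD ratio as well as on the correlation. If the setting targets are met, setting produces no shift.

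Four stronger readings might be inferred, and the documents do not support them:

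- *That baseline SBP is ignored.* It defines the 20% endpoint, and SBP contributes to the shock-index subgroups. It is only not used as a covariate.
- *That the plan commits to a patient-level test.* This is an inference from the plain two-group comparison and the sample size counted in patients; no unit or test is named.
- *That leaving out the covariates biases the result or inflates type I error.* It does neither.
- *That calendar date is not collected.* The text lists time of delivery, but it also refers to a separate data sheet that is not shown, so absence cannot be concluded.

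What remains is that the analysis as written does not follow the unit of assignment, and that a better method is available from data the trial already gathers.

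**Conclusion.** The concern holds in this limited form: no allowance for day of assignment, and baseline SBP and setting not used as covariates. On assumed inputs of 1 to 3 patients per day and ICC 0.01 to 0.05, true alpha would be about 0.051 to 0.068. The power forgone by not adjusting for baseline runs from nil at r 0.8 to about 4 to 5.5 points at r 0.3 if the SDs are equal. It is more if the post-drug SD is the smaller, and no upper bound can be set from the documents. These are modest effects, but the remedy is cheap and closes the choice of model before data are seen, so the change should be made. The alpha figures treat days as if assigned at random. The predictability of even/odd-day assignment is a separate weakness that no choice of model here removes.

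**What to change.** Prespecify as the primary analysis a two-sided logistic regression of the 20% fall on drug group, baseline SBP and setting (ED or pre-hospital), with standard errors clustered by calendar day and days counted across both settings.

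- Report a standardised risk difference with 95% CI, or an odds ratio if the named software cannot produce it, with the crude incidences alongside.
- Define one baseline, for example the mean of the two pre-drug readings, and use it for both the endpoint and the covariate.
- State whether the groups are as assigned by day or as treated. As assigned follows the allocation; the Primary Outcomes section words the groups by the drug with which RSI was done.
- Make sure the calendar date is in the dataset.

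**Cost.** Mostly wording, plus a check that SPSS can fit the model with clustered errors. The CI may widen by up to about 7% (√1.15 = 1.072). The robust test may reject slightly too often, up to about 0.06. Baseline adjustment may gain nothing if r is near 0.8.
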